2.6 Analysis of secondary efficacy objectives

2.6.1 Secondary endpoints

The secondary efficacy endpoints besides the primary decomposition as described above are:

1. Time from randomization to the occurrence of the first HF hospitalization or CV death;
2. Time from randomization to all-cause mortality.
3. Time from randomization to sudden death or resuscitated sudden cardiac arrest.
4. Number of visits to an ER due to HF that needs intravenous drugs.
5. Number of days alive out of the hospital within 1 year from randomization.
6. Recurrent events: number of HF hospitalizations and CV deaths.

2.6.2 Statistical hypothesis, model, and method of analysis

2.6.2.1 Analysis of time to events endpoints

The time from randomization to

- the first composite event of CV death or HF hospitalization,
- all-cause mortality, and
- to sudden death or resuscitated sudden cardiac arrest

will be analyzed using Cox's proportional hazards model with treatment as fixed-effect factor and stratified by country. The estimated hazards ratio and the corresponding 2-sided confidence interval will be provided for the FAS.

The Kaplan-Meier curves by treatment arm will be presented for the FAS. Additionally, the frequency and percentage of patients with a composite CV event will be provided by treatment arm.

Proportional hazard assumptions will be tested by weighted residuals diagnostics and by visual inspection. Alternative parametric survival models (Exponential, or Weibull, or Log-logistic, or log-normal survival models) will be used if

the risk proportional assumption did not meet. The model with the best likelihood function will be chosen in that case.

2.6.2.2 Analysis of number of visits to an ER due to HF that needs intravenous drugs

The rate of visits to an ER due to HF that needs intravenous drugs will be analyzed using a generalized linear model assuming a negative binomial distribution. The time at risk for a subject is the length of follow-up. The analysis model will include terms for treatment and country as fixed-effect factors and log (follow-up duration) as the offset. An estimate of the ratio of event rates between the treatment arms, together with the 95% confidence interval, will be presented for the FAS.

The number of visits to an ER due to HF that needs intravenous drugs during the treatment period will be summarized by treatment arms.

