#### 8.4.1 Laboratory evaluations

A central laboratory will be used for the efficacy analysis of NT-proBNP (at randomization and Week 12 visit). No reconciliation with the central laboratory will be done for the local NT-proBNP used during the screening epoch. Details on the collection, shipment of samples and reporting of results by the central laboratory are provided to Investigators in the laboratory manual.

For the remaining laboratory evaluations only local laboratory will be used. Laboratory values will not be entered in eCRF (except NT-proBNP from screening).

Clinically notable laboratory findings are defined in [Appendix 1](#).

Complete safety laboratory evaluations ([Table 8-3](#)) will be performed in the fasting state at the times indicated in [Table 8-1](#).

Study procedures may be performed without restriction while the local laboratory results are pending. In these cases, the Investigator or designee should review the local laboratory results

as soon as they become available to decide whether any adjustments in the participant's study drug or non-study drug regimen are needed.

The Investigator must assess laboratory values that exceed the boundaries of notable laboratory abnormality and perform additional laboratory evaluations as judged appropriate. If the laboratory abnormality is the primary reason for an unforeseen hospitalization or otherwise fulfills the seriousness category of an AE, then the procedure for rapid notification of SAEs must be followed. Likewise, if the laboratory abnormality leads to discontinuation from the study drug (temporarily or permanently), the participant must be followed until the abnormality resolves or until it is considered permanent. The investigation may include continued monitoring by repeat laboratory testing or by additional laboratory tests as deemed necessary by the Investigator or the ARO/Novartis medical monitor.

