2.6.2.3 Analysis of number of days alive out of the hospital

The duration in days of hospital-free survival within 1 year from randomization will be summarized by treatment group, and descriptive statistics (N, mean, standard deviation, median, and quartiles) will be provided. The mean difference between treatment groups will be compared using linear regression model with treatment as fixed factor adjusted for country. The estimated within treatment means, between-treatment difference and 95% confidence interval will be provided for FAS.

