2.11 Sample size calculation

An analysis of the 55 patients with Chagas' disease in the enalapril group in PARADIGM (Ramires et al 2018) showed an event rate of 20 events per 100 subject-years for CV death plus hospitalization due to HF. Similar event rates, for CV death plus hospitalization due to HF in CCC patients, has also been seen in the BENEFIT and SHIFT studies. Therefore, we assumed a rate of approximately 20 events per 100 subject-years for the CV event (composite of CV death and first HF hospitalization) for the enalapril group. Approximately 66% of the first CV events are HF hospitalizations. For the sample size calculation, we assumed a rate of 16 events per 100 subject-years for the sacubitril/valsartan group, which corresponds to an effect of 20%.

The sample size was determined based on a simulation study under the assumptions of:

- a one-sided type I error rate of 2.5%,
- a target power of 85%,
- a uniform accrual of 18 months,
- a study duration of 36 months, i.e. the individual follow-up times varied between 18 and 36 months,
- an annualized event rate of 0.16 for the composite of CV death or first HF hospitalization in the sacubitril/valsartan group, and an annualized event rate of 0.20 for the composite of CV death or first HF hospitalization in the enalapril group,
- a relative change of NT-proBNP between week 12 and baseline that is 25% lower in the sacubitril/valsartan group compared to the enalapril group

During the simulation study, a simulated trial was considered to show superiority of sacubitril/valsartan over enalapril when the win ratio was significantly larger than one based on the one-sided significance level of 2.5%, and the estimated hazard ratio of sacubitril/valsartan versus enalapril for time to first HF hospitalization was less than one, and the estimated hazard ratio of sacubitril/valsartan versus enalapril for CV death was less than one.

Based on these assumptions and criteria for superiority, a study with 900 patients results in the target power of 85%. Moreover, 302 participants with events for the composite of CV death or first HF hospitalization can be expected in the study.

As the primary hierarchical composite endpoint is evaluable as long as subject experience either a HF hospitalization, CV death, or have a NT-proBNP value measured at Week 12, the sample size calculation did not assume any loss of follow-up.

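### The secondary-endpoint models and the component Cox models omit baseline NT-proBNP; prespecifying it would add about 1 to 8 points to the roughly 49% power of the CV death or HF hospitalization composite

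*SAP*

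**What the plan says.** SAP 2.6.1 numbers six secondary efficacy endpoints. Their models are:

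- Composite, all-cause death, and sudden death or resuscitated arrest (SAP 2.6.2.1): a Cox "proportional hazards model with treatment as fixed-effect factor and stratified by country".
- ER visits for HF (SAP 2.6.2.2), negative binomial with a log follow-up offset: "The analysis model will include terms for treatment and country as fixed-effect factors".
- Days alive out of hospital within one year (SAP 2.6.2.3): a "linear regression model with treatment as fixed factor adjusted for country".
- Recurrent events (SAP 2.6.2.4): the LWYY model and a joint frailty model, with no covariates listed.

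The Cox models for CV death and for first HF hospitalization in SAP 2.5.3 also contain only treatment, stratified by country.

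Baseline NT-proBNP is a covariate in one place, the supportive ANCOVA of the NT-proBNP component (SAP 2.5.3). Protocol 8.5.1 plans the measurement at randomization for all main-study participants, and Protocol 8.4.1 says that "A central laboratory will be used for the efficacy analysis of NT-proBNP". SAP 2.5.2.3 expects some baseline values to be unavailable and substitutes a local screening value where one exists.

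**The concern.** The trial plans to collect, before treatment, a marker that it uses as an entry threshold and as part of its primary endpoint. It then leaves the baseline value out of every model for the clinical secondary endpoints. If the marker predicts those outcomes, a Cox model without it targets a hazard ratio nearer to 1 than the covariate-conditional one and has less power. The linear and count models without it give wider intervals than they need to.

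The composite of CV death or first HF hospitalization matters most here. It is the conventional clinical outcome beside which a win ratio partly decided by a biomarker will be read, and its power is modest.

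**Working it through.** **Inputs (SAP 2.11 and 1.1).** "an annualized event rate of 0.20 for the composite of CV death or first HF hospitalization in the enalapril group"; "an annualized event rate of 0.16 for the composite of CV death or first HF hospitalization in the sacubitril/valsartan group"; 450 per arm; uniform accrual over 18 months; 36 months in total; no loss to follow-up; one-sided 2.5%; 302 composite events.

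**The plan's own event count.** With rate λ, accrual of 1.5 years and analysis at 3 years, the probability of an event is 1 − [exp(−1.5λ) − exp(−3λ)]/(1.5λ).

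- Enalapril, λ = 0.20: 1 − (0.7408 − 0.5488)/0.30 = 0.3600; × 450 = 162.0.
- Sacubitril/valsartan, λ = 0.16: 1 − (0.7866 − 0.6188)/0.24 = 0.3006; × 450 = 135.3.
- Total 297.3 against the stated 302, or 1.6% lower. The figure reproduces.

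**Unadjusted power for the composite.** Schoenfeld: |ln 0.80| × √(302/4) = 0.2231 × 8.689 = 1.939. Then 1.939 − 1.960 = −0.021, which gives 49.2%. Freedman's formula gives 48.8%. By Schoenfeld, 80% power would need 631 events.

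**Effect of adjustment, Cox model.** The documents give no prognostic strength, so the hazard ratio per SD of log baseline NT-proBNP is an assumption. I simulated trials of 900 participants under the inputs above, 2,500 per row, without country strata. The Monte Carlo error of each power is about 1 point.

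| Assumed HR per SD | Power if the unadjusted HR is 0.80 | Power if the conditional HR is 0.80 |
|---|---|---|
| 1.3 | 48% → 49% | 47% → 48% |
| 1.5 | 48% → 52% | 46% → 49% |
| 1.75 | 49% → 54% | 43% → 48% |
| 2.0 | 49% → 56% | 42% → 50% |

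A separate run with 8,000 trials per row and an unadjusted HR of about 0.80 gave 48.7% → 50.0% at 1.35, 49.6% → 53.5% at 1.65 and 49.3% → 57.0% at 2.0. In that run the gain equals about 3%, 10% and 21% more events, or roughly 10, 31 and 63 on top of 302.

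**Where the gain comes from.** The standard error of the log hazard ratio was 0.116 to 0.117 with and without the covariate in every row. With an unadjusted HR of 0.80, the adjusted estimate averaged 0.798 at 1.3 per SD and 0.781 at 2.0. The estimate moves; its standard error does not.

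**Negative binomial model.** I simulated 900 participants, 400 trials per row, with a true rate ratio of 0.80 and an assumed control rate of 0.15 per year. Mean rate ratios unadjusted/adjusted were 0.817/0.816, 0.790/0.792 and 0.790/0.792 for covariate ratios of 1.35, 1.65 and 2.0 per SD. There is no attenuation. The standard error falls by 1%, 3% and 6%.

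**Linear model for days alive.** The residual variance shrinks by a factor of about 1 − R². The documents give no R², so no figure follows. No calculation was made for LWYY.

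**The case against.** The strongest reply is that nothing here is an error. Country-only models are valid for the effects they estimate and largely follow Protocol 12.5.1. Type I error control is stated only for the primary analysis (SAP 2.5.2), and the secondary results are estimates with intervals and no testing order. No formal decision therefore turns on the change, and the composite stays underpowered either way. All of this stands, and it limits the weight of the point. It does not answer why a planned baseline measurement, already accepted as a covariate in SAP 2.5.3, is left out elsewhere.

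A second reply is that some baselines will be missing. SAP 2.5.2.3 says so, Protocol 5.1 admits participants on BNP instead of NT-proBNP, and Protocol 8.4.1 does not reconcile local with central values. This stands too. A missing-value rule is needed, and a few covariate values will be local or imputed.

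A third is that SAP 2.1.2 names prior ACEI/ARB use as a randomization stratum, and no secondary model includes it. That is true, but it is a separate matter that this change does not settle.

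A reader might also infer more than the documents support:

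- That baseline NT-proBNP is the strongest prognostic factor, or is held for everyone. The only prognostic figure given concerns its change (Protocol 8.3.1: a 25% reduction with a 15% lower hazard), and SAP 2.5.2.3 contradicts complete availability.
- That all secondary endpoints have about 49% power. The documents project no counts for all-cause death or sudden death/arrest, and the 302 does not determine power for ER visits, days alive or recurrent events. At HR 0.80, 200 events would give 35% and 103 events 20%.
- That the ER-visit rate ratio is pulled towards 1. With a log link and randomized treatment it is not, as the simulation shows.

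**Conclusion.** The omission is real and worth correcting, but the gain is modest. For the composite, power of about 49% at 302 events and HR 0.80 rises by about 1 to 8 points, to roughly 49-57% if 0.80 is the unadjusted hazard ratio. If 0.80 is the conditional one, power after adjustment is 48-50%. The range rests on an assumed 1.3 to 2.0 per SD, and at the low end the gain is about one point.

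It would be wrong to describe the Cox gain as precision, since the standard error is essentially unchanged. Nor is the change free: the adjusted hazard ratio is conditional and differs slightly from the unadjusted one. The narrower interval belongs to the days-alive and ER-visit models. No size can be given for days alive, and for ER visits the only figure rests on an assumed event rate.

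**What to change.** Before unblinding, amend SAP 2.6.2.1 to 2.6.2.4 and 2.5.3 as follows.

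- Add log(baseline NT-proBNP) as a covariate to the secondary and component Cox models, the negative binomial ER-visit model, the linear days-alive model and the LWYY model, keeping country as planned. The joint frailty model can stay as it is, since its participant-level random effect already represents unexplained heterogeneity.
- If the central baseline is missing, use the local screening NT-proBNP as in SAP 2.5.2.3. If that is missing too, use the pooled median, so that nobody is dropped.
- Report the planned country-only estimate beside each adjusted one, and label the adjusted hazard ratio as conditional on baseline NT-proBNP.

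The cost is SAP wording and one model term, with no new data collection. The timing matters because an adjustment chosen after unblinding would be post hoc.

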#### **12.5.1.1 Analysis of the time to the occurrence of the composite CV outcome**

The time from randomization to the occurrence of the composite of CV death or first HF hospitalization will be analyzed using Cox's proportional hazards model with treatment and country as fixed-effect factors. The estimated hazards ratio and the corresponding 2-sided CI will be provided for the FAS.

The Kaplan-Meier curves by treatment arm will be presented for the FAS. Additionally, the frequency and percentage of participants with a composite CV event will be provided by treatment arm.

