2.13.2.3 Statistical hypothesis, model, and method of analysis

Summary statistics by treatment arm will be presented for each MRI measurement. Evaluations of all MRI measurement at 8-month will be performed adjusted for baseline values. The reduction of fibrosis and the improvement of cardiac structure after 8 months of treatment will be analyzed using generalized mixed linear models considering the hierarchical effect of study site and participant. Results will be graphically displayed in boxplots. Missing values will not be imputed; analyses will be performed on FAS populations, including only participants with available MRI data.

3 Change to protocol specified analyses

SAP second version includes the recurrent event as a key secondary endpoint, changed the number of days alive out of the hospital time definition changed to within 1 year from randomization, and the NT-ProBNP evaluation at month 8 was included as exploratory endpoint.

4 Appendix

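### The SAP's fallback for non-proportional hazards includes models that themselves assume proportional hazards, and otherwise changes the effect measure on the strength of the data

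*SAP*

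**What the plan says.** SAP 2.6.2.1 covers three secondary endpoints: the composite of CV death or HF hospitalization, all-cause mortality, and sudden death or resuscitated sudden cardiac arrest. Each "will be analyzed using Cox's proportional hazards model with treatment as fixed-effect factor and stratified by country", and "The estimated hazards ratio and the corresponding 2-sided confidence interval will be provided for the FAS".

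The assumption is then checked: "Proportional hazard assumptions will be tested by weighted residuals diagnostics and by visual inspection". No test level is given, and no rule for combining the test with the plots. The consequence of a failed check is that "Alternative parametric survival models (Exponential, or Weibull, or Log-logistic, or log-normal survival models) will be used if" the assumption does not hold, and "The model with the best likelihood function will be chosen in that case".

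The SAP does not state:
- which effect measure the replacement model reports;
- whether the Cox hazard ratio is still reported beside it;
- how country enters a parametric model;
- whether the Weibull shape may differ between arms.

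Protocol 12.5.1.1 to 12.5.1.3 contain no such switch. For the composite, the endpoint "will be analyzed using Cox's proportional hazards model with treatment and country as fixed-effect factors" and "The estimated hazards ratio and the corresponding 2-sided CI will be provided for the FAS"; the other two endpoints are treated alike. SAP section 3, on changes to the protocol's analyses, opens with "SAP second version includes the recurrent event as a key secondary endpoint" and goes on to days alive out of hospital and NT-proBNP at month 8. The parametric fallback is not listed.

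**The concern.** A fallback for failed proportional hazards should either drop that assumption or describe the effect in a way that does not need it. Two of the four candidates keep the assumption and add a restriction on the baseline hazard that Cox does not make. The other two drop it but leave the hazard-ratio scale.

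Both steps, the check by arm and the likelihood contest, use outcome data together with treatment codes. What is finally reported for each endpoint therefore depends on the data. Three results could come out on different scales, each with a confidence interval that ignores the two-step selection. SAP 2.9 also tests subgroup interactions in the models of section 2.6.2, so the undefined choice can carry over to subgroup results.

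**Working it through.** **Planning inputs (SAP 2.11).** Annual rates of 0.20 (enalapril) and 0.16 (sacubitril/valsartan), 450 per arm, uniform accrual over 1.5 years, total duration 3 years, no loss to follow-up. The documents give no figure for the fallback rule itself. The only related figure is the 302 expected participants with an event, reproduced here to confirm the simulation setting.

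Expected events per arm = 450 × [1 − (exp(−1.5λ) − exp(−3λ)) / (1.5λ)]
- Enalapril, λ = 0.20: 450 × [1 − (0.7408 − 0.5488)/0.30] = 162.0
- Sacubitril/valsartan, λ = 0.16: 450 × [1 − (0.7866 − 0.6188)/0.24] = 135.3
- Sum 297.3 against 302, a difference of 1.6%.

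**Step 1. What each candidate implies for the hazard ratio.** With treatment as a covariate and a common shape k, the Weibull hazard is k·t^(k−1)·exp(xb). The ratio between arms is exp(b) at every t. The exponential is the case k = 1. Illustration with a time ratio of 1.25 and assumed shapes, hazard ratio at each time:

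| Model | 0.25 y | 0.5 y | 1 y | 2 y | 3 y |
|---|---|---|---|---|---|
| Exponential | 0.80 | 0.80 | 0.80 | 0.80 | 0.80 |
| Weibull, shape 0.8 | 0.837 | 0.837 | 0.837 | 0.837 | 0.837 |
| Log-logistic | 0.81 | 0.82 | 0.83 | 0.85 | 0.87 |
| Log-normal | 0.80 | 0.83 | 0.86 | 0.88 | 0.89 |

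(Weibull: 1.25^(−0.8) = 0.837.) The first two rows are constant. The last two have no single hazard ratio; both models yield a time ratio, and the log-logistic also an odds ratio.

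**Step 2. The exponential cannot win.** It is the Weibull with k fixed at 1, so the maximised Weibull likelihood is at least as large in every data set.

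**Step 3. What best likelihood selects when hazards are not proportional.** Simulated trials: 450 per arm, enalapril rate 0.20, planned accrual and follow-up, hazard ratio changing at 6 months, no country effect. The scenarios are assumptions.

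All simulated trials, 300 per scenario:

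| Scenario (HR before, after 6 months) | Weibull | Log-logistic | Log-normal | Exponential |
|---|---|---|---|---|
| Delayed (1.0, 0.65) | 74% | 20% | 6% | 0% |
| Early (0.45, 1.0) | 56% | 44% | 0.3% | 0% |
| Crossing (1.4, 0.65) | 61% | 31% | 8% | 0% |

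Only trials that failed a residual-type test at p < 0.05, which is when the rule would act, 300 per scenario:

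| Scenario (HR before, after 6 months) | Weibull chosen |
|---|---|
| Delayed (1.0, 0.6) | 87% |
| Early (0.5, 1.0) | 57% |
| Crossing (1.3, 0.65) | 71% |

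The exponential was never chosen here either. Likelihood rewards overall fit, mostly of the baseline shape, and not a correct description of how the treatment effect varies over time. In these scenarios the rule rejects proportional hazards and then most often reports a model that assumes it.

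**The case against.** The strongest reply has four parts.

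**The rule is written down in advance.** The diagnostics, the candidates and the selection criterion are all in the SAP, and the protocol defers analysis detail to it. That is fair: this is not a free post hoc choice. But the trigger has no threshold and includes visual judgement, and a rule written in advance that selects the effect measure from the outcomes still gives a data-dependent estimand.

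**The text can be read more kindly.** The hazard ratio is promised without condition, so the Cox result might be kept beside the alternative. A Weibull with arm-specific shape is not a proportional-hazards model. Under a penalised criterion such as AIC the exponential could be selected. All three are true as statistics, but none is in the text.

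**The inferential effect is small.** In 400 simulated trials per scenario, among those failing a 5% test, the Cox z-statistic and that of the selected model correlated at 0.99 (delayed), 0.99 (early) and 0.97 (crossing). Two-sided 5% conclusions differed in about 3%, 4% and 5%. This stands, and it limits the point to the scale and meaning of the estimate.

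**The scope is narrow.** The rule acts only if the assumption is judged to fail, and planning used constant rates. The win ratio does not need proportional hazards, type I error control is stated only for the primary analysis, and the component Cox analyses in SAP 2.5.3 carry no fallback. All of this stands. A time-varying effect is nevertheless plausible: the target dose is reached only after about 6 weeks of titration (Protocol 3.2.1), and discontinuation, crossover and SGLT2 inhibitor use are all left in under treatment policy (SAP 2.12.1).

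**Conclusion.** The concern holds: the fallback is wrong as written. Of the four candidates, two (exponential, Weibull) do not address the violation, one of those two (exponential) cannot be selected by unpenalised likelihood, and two (log-logistic, log-normal) change the effect measure. This assumes the ordinary form of these models, with a common shape and treatment as a covariate, and likelihood taken literally.

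The 57% to 87% selection of Weibull rests on assumed scenarios with a change at 6 months and no country effect. It shows the direction of the problem and is not a forecast for this trial. All three time-to-event secondary endpoints are affected. The primary analysis, its alpha and the sample size are not, so there is no corrected number of participants or power to give. The change should be made, but it does not threaten the main conclusion of the trial.

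**What to change.** Amend SAP 2.6.2.1 before treatment codes are released:

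1. Delete the switch to parametric models and the best-likelihood rule.
2. State that the country-stratified Cox hazard ratio, with robust variance, is reported whatever the diagnostics show. If proportional hazards is doubtful, it is read as an average hazard ratio, which depends on the accrual and censoring pattern. Keep the residual check and plots as description only.
3. Because of that dependence, add one supplement in all cases: the difference in restricted mean survival time at a fixed horizon, with Kaplan-Meier differences at fixed times. Twenty-four months is an example. With uniform accrual over 18 months and a 36-month study, (36 − 24)/18 = 67% of participants would have at least 24 months of potential follow-up. The sponsor should confirm the horizon against the number at risk, without reference to treatment arm. Piecewise hazard ratios with stated cut points would be an acceptable alternative.
4. Record in SAP section 3 any departure from the protocol's Cox model that remains.

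The cost is a few sentences in the SAP and one standard extra analysis for each of the three endpoints. No new data are needed.
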